5.3. Determination of Sample Size

Approximately 960 patients will be randomized at a 1:1 ratio to ixekizumab and guselkumab. With 480 patients per treatment group, this study will have 98% power to test the superiority of ixekizumab to guselkumab for a 100% reduction in the Psoriasis Area and Severity Index (PASI 100) at Week 12. The following assumptions were used for the power calculation response rate at Week 12: 35.3% and 23.0% for the ixekizumab and guselkumab groups, respectively. A 2-sided Fisher's exact test at a significance level of 0.05 is assumed. This study is also powered at 95% to test the superiority of ixekizumab for PASI 100 at Week 24, assuming the response rate of ixekizumab and guselkumab at 56% and 44%, respectively. These assumptions are based on the ixekizumab and guselkumab clinical studies in psoriasis (Griffiths et al. 2015; Gordon et al. 2016; Blauvelt et al. 2017; Reich et al. 2017).

For the non-inferior test of PASI 100 at Week 24, a non-inferiority margin of -11.4% is considered sufficiently small to be clinically unimportant difference in outcome between guselkumab and ixekizumab. This non-inferior margin is based on a 70% retention rate approach assuming a placebo response rate of 6.0% at Week 24 observed in a phase 2 study (Deodhar et al. 2018). The sample size of 480 patient per treatment group provides >99% power to test the non-inferiority.

6. A Priori Statistical Methods

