6.14. Safety Analyses

Safety will be assessed by summarizing and analyzing AEs, laboratory analyses, vital signs, and Columbia-Suicide Severity Rating (C-SSRS). The duration of treatment exposure will also be summarized.

The primary safety analyses will focus on the comparison of ixekizumab to guselkumab for the Blinded Treatment Periods. For the Post-Treatment Follow-Up Period, safety data will be summarized according to the treatment which patients had received in the Blinded Treatment Periods.

All safety analyses will be conducted on the Safety Population.

Comparisons between treatment groups will be conducted using Fisher's exact test

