6.14.3.1. Special Safety Topics including Adverse Events of Special Interest

Safety information on special topics including AEs of special interest (AESI) will be presented by treatment. [Table RHCR.6.8](#) provides the definitions/derivations and analyses methods (including analyses, summaries and by-patient listings) of special safety topics including AESIs.

Potential AESIs will be identified by a standardized MedDRA query (SMQ) or a Lilly-defined MedDRA PT listing. Preferred terms within an SMQ will be classified as broad and narrow. In the Lilly-defined MedDRA PT listings, Lilly has provided the broad and narrow classification. The Lilly-defined broad terms are for a more sensitive search of potential events of interest and the Lilly-defined narrow terms are for a more specific search. Therefore, the summaries will include the classifications of broad term (same as pooling narrow and broad terms together) and narrow term.

In the event that the listing of terms or analysis changes for a special safety topic, it will be documented in the compound level safety standard (Program Safety Analysis Plan 2018) which will supersede this document; it will not warrant an amendment to the individual study SAP.

Fisher's exact tests will be used to compare the treatment groups for the safety population during the Blinded Treatment Periods.

Table RHCR.6.8. Definitions and Analyses of Special Safety Topics including Adverse Events of Special Interest

Special Safety Topic	Definition / Derivation	Analysis / Summary / Listing
Hepatic	
Hepatic AE analysis will include events that are potentially drug-related hepatic disorders by using the Medical Dictionary for Regulatory Activities (MedDRA) PTs contained in any of the following standardized MedDRA query (SMQ) or sub-SMQ as defined in MedDRA:
 
 • Broad and narrow terms in the Liver related investigations, signs and symptoms (20000008) • Broad and narrow terms in the Cholestasis and jaundice of hepatic origin (20000009) • Broad and narrow terms in the Hepatitis, non-infectious (20000010) • Broad and narrow terms in the Hepatic failure, fibrosis and cirrhosis and other liver damage (20000013) • Narrow terms in the Liver-related coagulation and bleeding disturbances (20000015) 	
Blinded Treatment Periods (Fisher’s exact test): TEAEs by PT within SMQ or sub-SMQ

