
Cytopenias
	
Cytopenias are defined using the PTs from the following 2 sub-SMQs of the Haematopoietic cytopenias SMQ (20000027) as specified in MedDRA:
 
 Broad and narrow terms in the Haematopoietic leukopenia (20000030) Broad and narrow terms in the Haematopoietic thrombocytopenia (20000031) 	
Blinded Treatment Periods (Fisher’s exact test): TEAEs by PT within sub-SMQ

Infections
	
Infections are events including all infections (defined using all the MedDRA PTs from the Infections and infestations SOC), serious infections, potential opportunistic infections (OIs), and infections resulting in anti-infective medication administration (i.e., antibacterial, antiviral, antifungal, antiparasitic treatment).
	
Blinded Treatment Periods (Fisher’s exact test): SAEs by PT, AEs leading to treatment discontinuation (including death) by PT, TEAEs by PT, TEAEs by maximum severity by PT

	
Anti-infective medications are defined in the compound level safety standard, including antibiotics, antifungals, antivirals, or antiprotozoals.
	
Listing: TEAE with anti-infective medications

	
The list of MedDRA terms used to identify infections that are pre-defined as potential OIs are found in the compound level safety standards. This list contains PTs as contained within Categories (narrow or broad) from the Infections and infestations SOC and from the Investigations SOC which can assist in identifying potential OIs. The narrow terms are considered opportunistic infections unless medical review determines that the reported term is not consistent with the patient’s clinical history/presentation/course. Medical review of broad terms is needed for final determination of patients meeting the program definition of OIs.
 
The number and percentage of patients with TEAEs that represent potential OIs and as potential OIs will be summarized by treatment group using MedDRA PT nested within categories. Events will be ordered by decreasing frequency in the ixekizumab group nested within categories.
	
Blinded Treatment Periods (Fisher’s exact test): TEAE of OIs by PT within Category
 
Listing: TEAE of OIs

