	
The duration of each common ($\geq 1\%$ of total ixekizumab) TEAE PT of Infections and narrow terms for OIs is defined as: Duration of treatment-emergent AE Infections (in weeks) = $(End\ date\ of\ AE - Start\ date\ of\ AE + 1) / 7.$ Patients who do not have the PT will not be included in the analysis. If the TEAE has not been reported as ended by the date of completion from the study, or date of early discontinuation, it will be censored as of that date. If a patient has multiple episodes of the same TEAE, the episode with the greatest severity will be used for the duration of event calculation. If a patient has multiple episodes of the same TEAE with the same severity, the episode with the longest duration will be used for the duration of event calculation.
	
Blinded Treatment Periods (Summary): Duration of common TEAEs- infections and narrow terms for opportunistic infections

Allergic Reactions/Hypersensitivities
	
Allergic reactions/hypersensitivity events will be categorized as either anaphylaxis or non-anaphylaxis events (these will refer to events that are not localized to the site of injection) and summarized separately. Medical reviews are needed for final determination of patients with allergic-reactions/hypersensitivities.
	
Blinded Treatment Periods (Fisher’s exact test): TEAE by PT within Category, TEAE by maximum severity by

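### The infection-duration summary picks its preferred terms by an ixekizumab-only 1% cut, so a term below 1% on ixekizumab is left out however common it is on guselkumab

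*SAP*

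**What the plan says.** The Infections entry of SAP Table RHCR.6.8 (Section 6.14.3.1) defines a duration in weeks for each common infection term. The parenthesis that defines common sets a floor of 1% "of total ixekizumab) TEAE PT of Infections and narrow terms for OIs is defined as". The output is listed as "Blinded Treatment Periods (Summary): Duration of common TEAEs- infections and narrow terms for opportunistic infections". Only patients with the event contribute: "Patients who do not have the PT will not be included in the analysis".

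The surrounding text is comparative. SAP Section 6.14 states: "The primary safety analyses will focus on the comparison of ixekizumab to guselkumab for the Blinded Treatment Periods". Section 6.14.3.1 adds: "Safety information on special topics including AEs of special interest (AESI) will be presented by treatment".

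The same Infections entry separately specifies Fisher's exact tests for "SAEs by PT, AEs leading to treatment discontinuation (including death) by PT, TEAEs by PT, TEAEs by maximum severity by PT". There, infections are "defined using all the MedDRA PTs from the Infections and infestations SOC", and no minimum frequency is set in either arm.

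**The concern.** The safety question is ixekizumab against guselkumab, and infections are a named adverse event of special interest (Protocol Section 9.2.1.2). A by-treatment table whose rows are chosen from one arm's counts treats the arms unequally. Two terms with the same imbalance in opposite directions can have different fates: the one that leans towards ixekizumab is displayed, and the one that leans towards guselkumab may not be.

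What is at stake is the duration information for one class of term, those below 1% on ixekizumab and at or above 1% on guselkumab. No other part of the SAP summarises infection duration, so for these terms it goes unreported in summary form. They are also terms for which the guselkumab arm would have usable data. Because the sponsor is comparing its own product with a competitor's, a symmetric rule is also easier to defend.

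**Working it through.** The documents state no derived figure on this point, so there is none to reproduce. The check turns the rule into a count and shows how it behaves.

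**Inputs**
- Rule: at least 1% on ixekizumab (SAP Table RHCR.6.8, Infections).
- Patients per arm: 480, from SAP Section 5.3 ("With 480 patients per treatment group, this study will have 98% power to test the superiority of ixekizumab to guselkumab"). The SAP does not define total ixekizumab. With one ixekizumab arm, it is taken here as that arm's safety population, assumed to be 480.
- True event rates: the documents give none for infections, so the rates below are assumptions.

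**Threshold as a count.** 0.01 × 480 = 4.8, so at least 5 ixekizumab patients are needed. The count stays at 5 for any ixekizumab safety population from 401 (4.01) to 500 (5.00), so it does not depend on the figure of 480 being exact.

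**Mirror-image example (hypothetical counts, ixekizumab vs guselkumab)**
- 4 vs 15: 4/480 = 0.8%, 15/480 = 3.1%. Below the cut on ixekizumab, so omitted.
- 15 vs 4: 3.1% and 0.8%. Above the cut, so shown for both arms.
- The two-sided Fisher p-value is 0.018 in either direction. Against 4 ixekizumab patients, the smallest guselkumab count with nominal p below 0.05 is 13 (2.7%, p = 0.047). That term would also be omitted from the duration summary, though not from the tested incidence table.

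**Chance that a term is omitted.** Let X and Y be the numbers of ixekizumab and guselkumab patients with the term, independent binomials with n = 480.
- Ixekizumab-only rule: P(X ≤ 4).
- Either-arm rule: P(X ≤ 4) × P(Y ≤ 4).

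| Assumed true rate, ixekizumab / guselkumab | Omitted, ixekizumab-only rule | Omitted, either-arm rule |
|---|---|---|
| 0.5% / 2% | 90.5% | 3.3% |
| 0.75% / 1.5% | 70.7% | 10.8% |
| 1% / 2% | 47.6% | 1.7% |
| 1.5% / 3% | 15.3% | 0.02% |
| 2% / 4% | 3.6% | under 0.001% |

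Worked first row: P(X ≤ 4) at 0.5% is 0.905, P(Y ≤ 4) at 2% is 0.036, and their product is 0.033. With those rates reversed (2% on ixekizumab, 0.5% on guselkumab), the present rule omits the term 3.6% of the time instead of 90.5%. The either-arm rule gives 3.3% in both directions.

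**Comparison within the SAP.** The injection-site-reaction entry of the same table has a duration summary with the same formula, censoring rule and choice of episode, but no frequency filter. Section 6.14.2 orders the general adverse event tables first by frequency in the overall group. An ixekizumab-only criterion is therefore not a convention that the SAP applies throughout.

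**The case against.** The strongest reply is that the comparison of infections is intact. The tests by preferred term use every infection term in both arms, opportunistic infections have their own Fisher's test, and all adverse events are listed by patient. A term seen in 4 and 15 patients would be counted, tested and graded by severity. This is correct, and it fixes the size of the point. A reader might infer that infections more common on guselkumab drop out of the head-to-head safety comparison. The documents do not support that, for two reasons:
- Being more common on guselkumab excludes nothing; only an ixekizumab rate below 1% does. At assumed true rates of 2% and 4%, the term is kept about 96% of the time and shown for both arms.
- The output concerned is a summary without a test.

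A reader might also infer that the displayed durations are biased. Selection is on how many ixekizumab patients had the term, not on how long it lasted, and each row uses only patients who had it. Nothing here shows a distortion within a row that is kept.

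Nor is it established that every row is chosen by frequency. Both the definition and the output label can be read as admitting narrow opportunistic-infection terms whatever their frequency.

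Two further replies carry less weight. Protocol Section 9.2.1.2 ties events of special interest to the safety and tolerability of ixekizumab, which could explain an ixekizumab-based cut. SAP Section 6.14.3.1 also lets a compound-level safety standard override the table, and that standard is not available here. Neither restores the missing duration summary under the plan as written, which presents special topics by treatment and gives comparison as the purpose.

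**Conclusion.** The point holds in a narrow form. The row-selection rule for the infection-duration summary depends on ixekizumab frequency alone. A term seen in 4 or fewer ixekizumab patients is omitted however many guselkumab patients had it, while its mirror image is kept. Only terms below 1% on ixekizumab and at or above 1% on guselkumab are affected, and only their appearance in one untested descriptive table. No efficacy result, error rate or tested safety comparison changes. This is an optional improvement, not a flaw in the trial's safety conclusions.

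The count of 5 rests on reading total ixekizumab as the ixekizumab safety population and on its size lying between 401 and 500. The omission probabilities rest on assumed event rates and on independence between arms; the asymmetry itself follows from the wording. If narrow opportunistic-infection terms are meant to be included regardless of frequency, the point applies only to the other infection terms.

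**What to change.** In the Infections entry of SAP Table RHCR.6.8, define common as at least 1% of patients in either treatment group of the safety population. In the same sentence, state whether the cut applies to narrow opportunistic-infection terms or whether these are always included.

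The cost is a few words in the SAP and a few more rows in one table. Data collection, sample size and tests are unaffected. SAP Section 6.14.3.1 already allows changes to a special-topic analysis to be recorded in the compound-level safety standard without amending the study SAP, so either document could carry it. It should be done before unblinding, because adding guselkumab-driven rows afterwards would be a post hoc choice.

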#### **9.2.1.2. Adverse Events of Special Interest**

The following adverse events of special interest (AESIs) will be used to determine the safety and tolerability of ixekizumab over the range of doses selected for this clinical study.

Adverse events of special interests for ixekizumab are the following:

- cytopenias (leukopenia, neutropenia, and thrombocytopenia)
- liver function test changes/enzyme elevations (ALT, AST, bilirubin, and ALP)
- infections
- injection-site reactions
- allergic reactions/hypersensitivities
- cerebro-cardiovascular events
- malignancies
- inflammatory bowel disease (IBD)
- depression

Sites will provide details on AEs as instructed on the eCRF. Investigators will also educate patients and/or caregivers about the symptoms of systemic allergic/hypersensitivity reactions and will provide instructions on the management and reporting of these reactions. Blood samples will be collected as soon as possible for any patient who experiences an AE of a potential

systemic allergic/hypersensitivity reaction during the study as judged by the investigator. These samples may be tested for ADAs, other laboratory tests needed to elucidate the cause of the allergic/hypersensitivity reaction, and/or ixekizumab serum concentration.

Data on preferred terms associated with cerebro-cardiovascular events (defined as death, cardiac ischemic event including MI and hospitalization for unstable angina, hospitalization for heart failure, serious arrhythmia, resuscitated sudden death, cardiogenic shock, coronary revascularization procedure, stroke/transient ischemic attack, peripheral revascularization procedure, peripheral arterial event, and hospitalization for hypertension) will be collected, and these events and any deaths will be adjudicated by an external Clinical Events Committee (CEC) made up of a chairperson, 2 cardiologists, and a neurologist.

Data on suspected IBD, as identified by events possibly indicative of ulcerative colitis and Crohn's disease, will be collected and the events will be adjudicated by an external CEC with expertise in IBD.

The role of the external CECs is to adjudicate defined clinical events in a blinded, consistent, and unbiased manner throughout the course of a study. The purpose of the CEC for adjudication of cerebro-cardiovascular events and the CEC for adjudication of suspected IBD events is to ensure that all reported events are evaluated uniformly by a single group.

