
Cerebro-cardiovascular Events
	
Cerebro-cardiovascular events will be externally adjudicated by the Central Events Committee (CEC) at the Cleveland Clinic, as outlined in the Manual of Operations. The CEC will adjudicate investigator-reported events selected for adjudication and render an assessment as to whether the event represents a confirmed event (meeting the event definition with all necessary documentation), a non-event (does not meet the event definition and likely represents an alternative or nonevent diagnosis), or lacks sufficient documentation for confirmation of an event. All events selected by investigator for CEC adjudication will be used for the analysis of cerebro-cardiovascular events. The categories of adjudicated events used for the analysis will include the following:
 
 • Cardiovascular 
 ○ Death (Cardiovascular) ○ Myocardial Infarction (MI) ○ Hospitalization for Unstable Angina ○ Hospitalization for Heart Failure ○ Serious Arrhythmia ○ Hospitalization for Hypertension ○ Resuscitated Sudden Death ○ Cardiogenic Shock due to Myocardial Infarction ○ Coronary Revascularization • Neurologic 
 ○ Cerebrovascular Event: Transient Ischemic Attack or Stroke (Hemorrhagic, Ischemic, and Undetermined) • Peripheral Vascular Events 
 ○ Peripheral Arterial Event ○ Peripheral Revascularization 
Events will be analyzed using MedDRA PT nested within the CEC assessment (confirmed event, no event, or insufficient documentation for event determination) and the subcategory. Subtypes of stroke (Hemorrhagic Stroke , Ischemic Stroke, and Undetermined Stroke Type) will be displayed in the analyses nested within Cerebrovascular Event. Subtypes of Serious Arrhythmia (Atrial Arrhythmia, Ventricular Arrhythmia, Heart Block, Other, Unknown) will be displayed nested within Serious Arrhythmia.
	
Blinded Treatment Periods (Fisher’s exact test): TEAE by PT within Subcategory

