
Major Adverse Cerebro-cardiovascular Events (MACE)
	
MACE (requiring adjudication as defined above) is defined as:
 
 • Vascular death (including cardiovascular and cerebro-vascular causes excluding hemorrhagic deaths outside of the central nervous system) • Non-fatal myocardial infarction • Non-fatal stroke (subcategories: ischemic, hemorrhagic, unknown stroke type) 
Where,
 
 • Vascular death should be captured as an Event on Adjudication - Death eCRF page with Adjudication Death Type = “Cardiovascular.” • Non-fatal myocardial infarction should be captured as an Event on Adjudication - Cardiac Ischemic Event eCRF page with Type of Ischemic Event = “Myocardial Infarction” and the Event is NOT on Adjudication - Death eCRF page. • Non-fatal strokes (ischemic, hemorrhagic) should be captured as an Event on Adjudication - Cerebrovascular Event eCRF page with Stroke Cerebrovascular Event Subtype in one of the following categories: hemorrhagic stroke, ischemic stroke, undetermined stroke type, and the Event is NOT on Adjudication - Death eCRF page. Subcategories of non-fatal stroke (Hemorrhagic Stroke, Ischemic Stroke, and Undetermined Stroke Type) will be displayed nested within non-fatal stroke category. 	
Blinded Treatment Periods (Fisher’s exact test): TEAE by maximum severity by PT within Category

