Inflammatory Bowel Disease (IBD)	IBD will be identified based on adjudication results. IBD will be also presented according to the following subcategory and MedDRA PTs. IBD Specific Terms (Narrow terms): 
 • Inflammatory Bowel Disease: Inflammatory bowel disease • Crohn’s Disease: Crohn’s disease • Ulcerative Colitis: Acute haemorrhagic ulcerative colitis; Colitis ulcerative; Proctitis ulcerative IBD Non-Specific Terms: The PTs in this category are listed in the compound level safety standard.	Blinded Treatment Periods (Fisher’s exact test): TEAE by PT within Subcategory

Abbreviations: AE = adverse event; eCRF = electronic case report form; FEAE = follow-up emergent adverse event; HLT = high-level term; PT = preferred term; SAE = serious adverse event; SOC = System Organ Class; TB = tuberculosis; TEAE = treatment emergent adverse event.

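### A listed cerebro-cardiovascular event or a death that the investigator does not select for adjudication may be missing from the SAP's CV and MACE tables, although the protocol sends all listed events and any deaths to the committee

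*SAP*

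**What the plan says.** Protocol 9.2.1.2 sets out which events are captured: "Data on preferred terms associated with cerebro-cardiovascular events (defined as death, cardiac ischemic event including MI and hospitalization for unstable angina", followed by further types such as hospitalization for heart failure, serious arrhythmia, cardiogenic shock, stroke and peripheral arterial events. It continues that "these events and any deaths will be adjudicated by an external Clinical Events Committee (CEC"). The purpose of the committee "is to ensure that all reported events are evaluated uniformly by a single group".

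The CV row of SAP Table RHCR.6.8 (Section 6.14.3.1) opens by saying that CV events are adjudicated externally under a Manual of Operations. It then says: "The CEC will adjudicate investigator-reported events selected for adjudication". After naming the three possible rulings (confirmed, non-event, insufficient documentation), it says: "All events selected by investigator for CEC adjudication will be used for the analysis of cerebro-cardiovascular events". The list of categories begins: "The categories of adjudicated events used for the analysis will include the following".

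The next row begins: "MACE (requiring adjudication as defined above) is defined as". It takes vascular death, non-fatal MI and non-fatal stroke from adjudication eCRF pages.

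The inflammatory bowel disease row differs. It relies on adjudication, but adds: "IBD will be also presented according to the following subcategory and MedDRA PTs".

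**The concern.** The two documents describe the set of events by different routes. In the protocol, an event goes to the committee because of its type, and a death because it is a death. In the SAP, an event reaches the committee, and then the table, because the investigator selected it. If sites apply different thresholds for selection, the tabulated events depend in part on site judgement, which central adjudication is meant to make uniform.

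The omission would also be hard to see. The CV table nests events under the three committee rulings. It has no line for qualifying events that were never submitted, and neither the CV row nor the MACE row describes a term search to find them.

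What is at stake is the completeness of two tables of rare, serious events in a head-to-head comparison, each with its own Fisher's exact test.

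**Working it through.** The plan states no expected CV or MACE count, so there is no figure of its own to reproduce. The check is a comparison of texts, followed by a rough size.

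**Texts side by side**

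1. *What goes to the committee.* Protocol 9.2.1.2: the listed events and any deaths. SAP CV row: investigator-reported events that were selected.
2. *What enters the CV table.* The SAP says that all selected events are used, in categories of adjudicated events. It names no other source.
3. *What enters MACE.* Adjudication as in the CV row, read from adjudication eCRF pages. An event or death never submitted would have no entry there.
4. *Is there a backstop?* Protocol 10.3.4.1 and the opening of SAP 6.14.3.1 both say that potential AESIs are identified by a standardized MedDRA query or a sponsor-defined preferred-term listing. CV events are an AESI in Protocol 9.2.1.2. Every other row of Table RHCR.6.8 has a MedDRA or laboratory definition. The IBD row pairs adjudication with preferred terms, and the injection-site row pairs investigator-identified events with a MedDRA high-level term. The CV and MACE rows have no such search.
5. *Where would an unselected event still appear?* If treatment-emergent, in the TEAE tables (SAP 6.14.2). If serious, in the SAE tables (SAP 6.14.3). All deaths during participation are in the by-patient listing (SAP 6.14.3).
6. *Category labels.* The protocol lists cardiogenic shock without a cause; the SAP category is limited to shock due to myocardial infarction. This is a separate, minor mismatch.

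**Rough size**

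- Inputs: 960 randomised (Protocol 5.2 and 10.1; SAP 5.3). Week 24 is day 168 (Protocol Section 2), and the exposure formula adds one day (SAP 6.14.1), giving 169 days. The event rate is an assumption: 0.5 to 2 per 100 patient-years.
- Patient-years = 960 × 169 / 365.25 = 444. This is an upper figure, because it ignores the 5% dropout anticipated in Protocol 5.2.
- Expected events = 444 × 0.005 = 2.2, up to 444 × 0.02 = 8.9.
- One omitted event as a share of the total = 1/8.9 = 11%, up to 1/2.2 = 45%.

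**Effect on a comparison (illustrative counts only).** With 480 per arm, the two-sided Fisher p-value is 0.031 for 6 versus 0 events and 0.062 for 5 versus 0. At such low counts, one event can decide which side of 0.05 the result falls. The counts were chosen to show this and are not a forecast.

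**The case against.** Much of the case on the other side stands.

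- *The SAP does not restrict the analysis in so many words.* A reader might infer that the SAP excludes unselected events outright. The sentence is inclusive in form, and its place after the three rulings suggests that its job is to keep events the committee did not confirm. That is a fair reading. It still supplies no route for an event that was not selected, and an earlier sentence in the same row describes adjudication itself as applying to selected events.
- *The Manual of Operations may settle it.* If it requires sites to submit every listed event and every death, the two sets coincide. The protocol itself says these will be adjudicated, and the SAP does not say that sites may withhold them. This is why the loss is possible and not established.
- *Deaths.* A reader might infer that deaths of unclear cause are held back. The documents do not say so. The MACE row selects deaths by an adjudicated type field, which suggests that deaths of several types are submitted and then classified. Non-cardiovascular deaths are outside MACE by definition.
- *The protocol gives no term list.* It speaks of preferred terms associated with the events, but several listed types, such as serious arrhythmia, are clinical definitions. A programmed search is therefore an addition consistent with the general AESI rule, and goes beyond restoring protocol text.
- *Nothing disappears from the report.* Most listed types would be serious, so they would be tabulated elsewhere with a treatment comparison. Those tables are not adjudicated, however, and do not feed the CV or MACE rows.
- *Bias between arms.* A reader might infer a distorted comparison. Investigators and outcome assessors are blinded (Protocol 5.1 and 7.4), and the documents offer no mechanism for selection to differ by arm. The risk is an undercount. The safety tests carry no multiplicity adjustment (SAP 6.4) and have no confirmatory role.

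**Conclusion.** The mismatch between Protocol 9.2.1.2 and SAP Table RHCR.6.8 is real. On the SAP text, a qualifying event or death that is not selected may be missing from the CV and MACE tables while remaining in the general TEAE and SAE tables or the death listing. The frequency is unknown. One omission would be about 11% to 45% of all events, but only under the assumed rate of 0.5 to 2 per 100 patient-years and full follow-up of 960 patients. The documents give neither a rate nor any indication of how likely an omission is.

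This is an ascertainment risk in secondary safety tables and does not touch the primary endpoint. It should be corrected because the events are serious and few and the correction is cheap.

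**What to change.** In Table RHCR.6.8:

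1. State that all events of the types listed in Protocol 9.2.1.2, and all deaths, are submitted to the committee and enter the CV analysis under its ruling, whether or not the investigator selected them. State that MACE is derived from that set.
2. Add a programmed preferred-term reconciliation, using a sponsor-defined term list as for other AESIs. It should refer unselected candidate events to the committee and report the number of qualifying events not adjudicated.
3. Reconcile the cardiogenic shock category with the protocol, or give the reason for the narrower one.

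The cost is a few sentences in the SAP, a term list, some programming, and a few more cases for a committee that already exists. If the Manual of Operations already requires full submission, the first change only records that in the SAP.
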